# Proprietary Information of MD Anderson

Protocol # 2016-0251

Date: February 24, 2020

114

Endpoint/Variable (Description, Time Point)	Statistical Method	Analysis Population	Missing Data Approach
Biomarkers and Safety/tolerability	exact method based on binomial distribution (Clopper-Pearson method)	ASaT	Subjects with missing data are considered non-responders
Key Secondary/Exploratory Endpoints			
DOR – RECIST 1.1 by M.D. Anderson radiology	Summary statistics using Kaplan-Meier method, if sample size permits	All responders	Non-responders are excluded from analysis. Responders are censored according to the censoring rules listed in Table 18.
DCR – RECIST 1.1 by M.D. Anderson radiology	Exact method based on binomial distribution (Clopper-Pearson method)	ASaT	Subjects with missing data are considered as subjects with disease not under control
TTP – RECIST 1.1 by M.D. Anderson radiology	Summary statistics using Kaplan-Meier method	ASaT	Censored at last assessment
PFS – RECIST 1.1 by M.D. Anderson radiology	Summary statistics using Kaplan-Meier method	ASaT	Censored at last assessment
OS	Summary statistics using Kaplan-Meier method	ASaT	Censored at last known alive date

Table 18 Censoring Rules for DOR

Situation	Date of Progression or Censoring	Outcome
No progression nor death, no new anti-cancer therapy initiated	Last adequate disease assessment	Censor (non-event)
No progression nor death, new anti-cancer therapy initiated	Last adequate disease assessment before new anti-cancer therapy initiated	Censor (non-event)
Death or progression after $\geq 2$ consecutive missed adequate disease assessments	Last adequate disease assessment prior to the after $\geq 2$ consecutive missed adequate disease assessments	Censor (non-event)
Death or progression after $\leq 1$ missed adequate disease assessments	PD or death	End of response (Event)

Subjects are considered to have an ongoing response if censored, alive, have not progressed, have not started a new anti-cancer therapy and have not been determined to be lost to follow-up.

## 8.6.2 Statistical Methods for Safety Analyses

Safety and tolerability will be assessed by clinical review of all relevant parameters including AEs, laboratory tests, and vital signs.

Counts and percentages of subjects with AEs will be provided. Analysis of AEs will be descriptive.

Bayesian toxicity monitoring will be performed to ensure that treatment is safe. Dose-limiting toxicity (DLT) is defined as Grade 3 or higher non-hematologic toxicity or Grade 4 or higher hematologic toxicity as per below. DLTs will be assessed during the first cycle of combination therapy. A DLT rate of 30% or higher is considered excessive. We will hold the patient enrollment if the probability of excessive toxicity is high (i.e.,  $\text{Prob}(\text{DLT} > 0.3) > 0.8$ ). This corresponds to withhold new patient entry when 3 DLTs are observed in 5 to 6 patients, 4 DLTs in 7 to 9 patients, 5 DLTs in 10 to 12 patients, or 6 DLTs in 13 to 14 patients, respectively. The probability of withholding new patients upon entry (early stopping) is 0.02, 0.15, 0.41, 0.68, and 0.88 if the true DLT rates are 0.1, 0.2, 0.3, 0.4, and 0.5, respectively. The calculation assumes that the prior distribution of the probability of DLT is beta(0.5, 0.5).

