Duration of Participation	Each subject will participate in the trial from the time the subject signs the ICF through the final contact. After a screening phase of up to 28 days, each subject will receive pembrolizumab beginning on Day 1 of each 3-week dosing cycle. Treatment will continue until progressive disease, unacceptable adverse events (AEs), intercurrent illness that prevents further administration of treatment, investigator's decision to withdraw the subject, subject withdrawal of consent, pregnancy of the subject, noncompliance with trial treatment or procedure requirements, subject receives 35 treatments (approximately 2 years) of pembrolizumab, or administrative reasons requiring cessation of treatment. Subjects who discontinue for reasons other than progressive disease will have post-treatment follow-up visits for monitoring disease status until progressive disease, initiating a non-study cancer treatment, withdrawing consent from study participation, or becoming lost to follow-up. All subjects will be followed (by telephone or visit) for overall survival until death, withdrawal of consent from study participation, or the end of the study. After the end of study treatment, each subject will be followed for 30 days for adverse event monitoring. Serious AEs (SAEs) will be collected for 90 days after the end of treatment or for 30 days after the end of treatment if the subject initiates new anticancer

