### 5.2.1.2 Dose Modification and Toxicity Management Guidelines for Pembrolizumab

AEs associated with pembrolizumab exposure may represent an immunologic etiology. These immune-related AEs (irAEs) may occur shortly after the first dose or several months after the last dose of pembrolizumab treatment and may affect more than one body system simultaneously. Therefore, early recognition and initiation of treatment is critical to reduce complications. Based on existing clinical study data, most irAEs were reversible and could be managed with interruptions of pembrolizumab, administration of corticosteroids and/or other supportive care. For suspected irAEs, ensure adequate evaluation to confirm etiology or exclude other causes. Additional procedures or tests such as bronchoscopy, endoscopy, skin biopsy may be included as part of the evaluation. Based on the severity of irAEs, withhold or permanently discontinue pembrolizumab and administer corticosteroids. Dose modification and toxicity management guidelines for irAEs associated with pembrolizumab are provided in Table 6.

Table 6 Dose modification and toxicity management guidelines for immune-related AEs associated with pembrolizumab

General instructions:				
irAEs	Toxicity grade or conditions (NCI CTCAE v4.0)	Action taken to pembrolizumab	irAE management with corticosteroid and/or other therapies	Monitor and follow-up
Pneumonitis	Grade 2	Withhold	
 
Administer corticosteroids (initial dose of 1-2 mg/kg prednisone or equivalent) followed by taper
 
	
 
Monitor subjects for signs and symptoms of pneumonitis
 
Evaluate subjects with suspected pneumonitis with radiographic imaging and initiate corticosteroid treatment
 
Add prophylactic antibiotics for opportunistic infections
 

	Grade 3 or 4, or recurrent grade 2	Permanently discontinue		

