### **5.2.1.4 Zepatier Dose Modification (Escalation/Titration/Other)**

Dose modification of Zepatier is not permitted with the exception of hepatic events, SAEs, or laboratory abnormalities.

During clinical trials with Zepatier with or without RBV, 1% of subjects experienced elevations of ALT from normal levels to greater than  $5 \times$  ULN, generally at or after treatment week 8. ALT elevations were typically asymptomatic and most resolved with ongoing or completion of therapy. Higher rates of late ALT elevations occurred in the following subpopulations: female sex (2% [10/608]), Asian race (2% [4/164]), and age 65 years or older (2%). For ALT elevations on Zepatier, follow recommendations in full prescribing information.

Hepatic laboratory testing should be performed prior to therapy, at treatment Week 8, and as clinically indicated. For patients receiving 16 weeks of therapy, additional hepatic laboratory testing should be performed at treatment week 12.

- Subjects should be instructed to consult their healthcare professional without delay if they have onset of fatigue, weakness, lack of appetite, nausea and vomiting, jaundice, or discolored feces.
- Consider discontinuing Zepatier if ALT levels remain persistently greater than  $10 \times$  ULN.
- Discontinue Zepatier if ALT elevation is accompanied by signs or symptoms of liver inflammation or increasing conjugated bilirubin, ALP, or INR.

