### 8.6.2.1 Definition of Dose-Limiting Toxicities

All toxicities will be graded using National Cancer Institute (NCI) CTCAE Version 4.0 (Appendix 12.7).

The occurrence of any of the following toxicities during Cycle 1 will be considered a DLT, if judged by the Investigator to be possibly, probably or definitely related to study treatments.

1. Grade 4 hematologic toxicity lasting  $\geq 14$  days.
2. Grade 4 non-hematologic toxicity (not laboratory).
3. Grade 3 non-hematologic toxicity (not laboratory) lasting  $> 3$  days despite optimal supportive care except inadequately treated hypersensitivity reactions
4. Any Grade 3 or higher non-hematologic laboratory value if:
  - Medical intervention is required to treat the subject, or
  - The abnormality leads to hospitalization, or
  - The abnormality persists for  $> 1$  week.
5. Febrile neutropenia Grade 3 or Grade 4:
  - Grade 3 is defined as ANC  $< 1000/\text{mm}^3$  with a single temperature of  $> 38.3$  degrees C (101 degrees F) or a sustained temperature of  $\geq 38$  degrees C (100.4 degrees F) for more than one hour.
  - Grade 4 is defined as ANC  $< 1000/\text{mm}^3$  with a single temperature of  $> 38.3$  degrees C (101 degrees F) or a sustained temperature of  $\geq 38$  degrees C (100.4 degrees F) for more than one hour.

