# Proprietary Information of MD Anderson

Protocol # 2016-0251

Date: February 24, 2020

116

degrees F) for more than one hour, with life-threatening consequences and urgent intervention indicated.

6. Thrombocytopenia <25,000/mm^3 if associated with:
  - A bleeding event which does not result in hemodynamic instability but requires an elective platelet transfusion, or
  - A life-threatening bleeding event which results in urgent intervention and admission to an Intensive Care Unit.
7. Grade 5 toxicity (i.e., death).
8. Delay in the scheduled administration of any component of therapy (IPI, PEG-INF, MK-3475) of >14 days
9. A delay of > 1 week due to drug-related toxicity in initiating Cycle 2.
10. Unable to complete at least 80% of any of the three treatments during the first course of therapy due treatment-related toxicity (even if not meeting above DLT criteria).

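### The Arm B enrolment hold counts only Cycle 1 toxicity, so it cannot register liver toxicity that first appears later in the 12 to 16 week Zepatier course

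*Combined protocol and SAP*

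**What the plan says.** Section 8.6.2 gives the purpose of the rule: "Bayesian toxicity monitoring will be performed to ensure that treatment is safe". It adds that "A DLT rate of 30% or higher is considered excessive", and enrolment is held when Prob(DLT rate > 0.3) exceeds 0.8 under a beta(0.5, 0.5) prior. The window is fixed in the same paragraph ("DLTs will be assessed during the first cycle of combination therapy") and again in Section 8.6.2.1: "The occurrence of any of the following toxicities during Cycle 1 will be considered a DLT". Section 1.0 gives the cycle length: "each subject will receive pembrolizumab beginning on Day 1 of each 3-week dosing cycle".

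The DLT item that reaches furthest is item 9 of Section 8.6.2.1, "A delay of > 1 week due to drug-related toxicity in initiating Cycle 2". It extends the view to about week 4 (3 weeks plus 1).

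Two other sections describe later toxicity. Section 5.2.1.4 says ALT rises above 5 x ULN on Zepatier came "generally at or after treatment week 8". Section 5.2.1.2 says immune-related events "may occur shortly after the first dose or several months after the last dose of pembrolizumab treatment". Section 4.3.2 says that treating HCV during active systemic therapy for HCC has not been studied.

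**The concern.** Safety and tolerability is a primary endpoint, and Arm B combines two treatments that can each affect the liver, in subjects with Child-Pugh A disease. The one rule that turns an observed toxicity rate into an enrolment decision stops looking at week 3 or 4. If the combination produced a high rate of liver events from week 8 onward, Arm B could fill to 15 subjects without any boundary being crossed. The stopping probabilities in Section 8.6.2 could still be quoted as evidence that toxicity had been monitored, with nothing in the text saying that they refer to Cycle 1 alone.

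**Working it through.** **1. Reproduce the plan's rule.** The inputs are from Section 8.6.2. With x DLTs in n subjects, the posterior is Beta(0.5 + x, 0.5 + n − x), and the boundary is the smallest x with Pr(p > 0.3) > 0.8.
- n = 5: x = 2 gives 0.703 and x = 3 gives 0.923, so the boundary is 3. At n = 6, x = 3 gives 0.857.
- n = 7: x = 3 gives 0.778 and x = 4 gives 0.936, so it is 4. At n = 9, x = 4 gives 0.830.
- n = 10: x = 4 gives 0.762 and x = 5 gives 0.912, so it is 5. At n = 12, x = 5 gives 0.814.
- n = 13: x = 5 gives 0.754 and x = 6 gives 0.895, so it is 6. At n = 14, x = 6 gives 0.853.

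These are the plan's boundaries. An exact binomial recursion with a look after each subject from n = 5 to n = 14 gives:

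| True DLT rate | Plan | Recomputed |
|---|---|---|
| 0.1 | 0.02 | 0.020 |
| 0.2 | 0.15 | 0.147 |
| 0.3 | 0.41 | 0.398 |
| 0.4 | 0.68 | 0.676 |
| 0.5 | 0.88 | 0.875 |

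Agreement is within 0.02, so the rule is correctly calculated for what it counts.

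**2. What it does not count.** An event with onset at week 8 has x = 0 in the Cycle 1 count. If all toxicity is late, P(hold) is 0 whatever the late rate.

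**3. Documented single-agent rates.** Section 5.2.1.4 gives 1% for Zepatier ALT rises (2% in named subgroups). Section 5.2.1.3 gives about 1% for immune-related hepatitis on pembrolizumab. With the same boundaries, and late events counted before the next entry, P(hold) at a true rate of 1-2% is at most 0.0002. Lengthening the window changes nothing in practice at these rates.

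**4. Unknown combination rate.** The documents give no figure, so late rates of 10% to 50% are assumed. The other assumptions are:
- 15 subjects over 13.5 months (midpoint of the 12-15 months in Section 1.0);
- late events spread over weeks 8 to 16;
- a 16-week course for all;
- looks at each new entry, starting at n = 5 with the listed boundaries.

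Accrual is then 13.5 × 52/12 = 58.5 weeks for 15 subjects, or 3.9 weeks per subject. About 16/3.9 ≈ 4 subjects are still under observation at each look, so the denominator convention matters. With events counted at once and non-events at course end, simulation gives:

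| Assumed late rate | Cycle 1 rule | Separate hepatic monitor |
|---|---|---|
| 10% | 0 | 0.02 |
| 20% | 0 | 0.14 |
| 30% | 0 | 0.37 |
| 40% | 0 | 0.61 |
| 50% | 0 | 0.82 |

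With all enrolled subjects as the denominator the figures are lower: about 0.19 at 30% and 0.66 at 50%.

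**5. Why a minimum n is needed.** Under beta(0.5, 0.5), 1 event in 1 subject gives Pr(p > 0.3) = 0.92, already above 0.8. With no minimum, the hepatic monitor would hold with probability 0.14-0.22 at a true 10% rate. Starting at n = 5 and counting only related events brings this to about 0.02-0.03.

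**The case against.** Four points can be made for the plan.

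**The documented late signal is small.** Section 5.2.1.4 describes a 1-2% event, typically without symptoms and mostly resolving. A reader might infer that a longer window would have caught the known Zepatier effect; step 3 shows that it would not. This stands, and it limits the point to the unknown rate of the combination.

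**Early liver toxicity is plausible too.** A reader might infer that most of the combination's liver toxicity falls after Cycle 1. The documents do not show this. Section 4.3.2 reports transaminitis on tremelimumab most often after the first dose, and transaminitis after a single dose of nivolumab in chronic HCV. Section 5.2.1.2 allows early as well as late immune-related events and gives no distribution. Section 6.1 schedules weekly liver panels in the first two cycles. An early window is reasonable, but it is not sufficient alone.

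**Late events are not unmonitored.** It would be wrong to read the plan that way. Hepatic events of clinical interest require holding pembrolizumab and notifying Merck within 24 hours (Sections 5.2.1.3 and 7.2.4.2). Zepatier has its own ALT criteria and hepatic tests at week 8, and at week 12 for 16-week regimens (Section 5.2.1.4). Section 7.2.4.3 has the investigator review aggregated safety data, and Section 5.9 permits early termination. But the first two act on individual subjects, and the last two carry no threshold. Section 8.7 makes DLT analysis continuous but keeps the Cycle 1 definition. The summary in Section 10.6 is due only after 15 subjects have completed treatment.

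**A second formal boundary may be more than a small open-label arm needs.** This is a matter of judgement. It weighs less here because the data are already collected.

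**Conclusion.** The point holds as a limit on the scope of the rule; its arithmetic is sound. For liver toxicity that first appears after about week 4, the enrolment hold has probability 0 of responding at any rate. A separate monitor over the Zepatier course would respond with probability about 0.37 at an assumed 30% late rate and 0.82 at 50%, or about 0.19 and 0.66 if all enrolled subjects form the denominator. These figures rest on assumed late rates, event timing and accrual. The documents give no late hepatic rate for the combination and do not suggest that 30% or 50% is likely. The case for change is that the rate is unknown, safety is a primary endpoint, and no other safeguard sets a number. It is a worthwhile, inexpensive improvement to Arm B monitoring.

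**What to change.** For Arm B, keep the Cycle 1 rule and add to Section 8.6.2 a second run of the same monitor, with a beta(0.5, 0.5) prior and a hold if Prob(rate > 0.3) > 0.8.
- **Event:** a treatment-related hepatic toxicity of Grade 3 or higher, or a treatment-related hepatic event of clinical interest as defined in Section 7.2.4.2, excluding those attributed to HCC progression. That section's criteria require no relatedness, and ascites, variceal bleeding or a bilirubin rise can come from the tumour, so the restriction is needed if the 30% limit set for related DLTs is to be reused.
- **Window:** first dose to the end of the subject's Zepatier course.
- **Looks:** from n = 5, with the listed boundaries.
- **Denominator:** state how subjects still under observation are counted. Counting events at once and non-events at course end leans towards holding; using all enrolled subjects leans the other way.
- **Reporting:** give this monitor's own stopping probabilities under the chosen convention, and label the existing 0.02 to 0.88 as applying to Cycle 1 toxicity only.

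The cost is SAP wording and a short simulation. Liver panels are already drawn every cycle, and hepatic events of clinical interest already go to Merck within 24 hours. The downsides are an added false-hold chance of about 0.02-0.03 at a true 10% rate and a lag of up to 16 weeks before a non-event enters the denominator. If the second monitor is not adopted, the labelling sentence should still be added.

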This trial aims to test pembrolizumab as monotherapy and in combination with additional agents to assess safety and efficacy in HCC. It will commence as a single-arm, open-label, single-site Phase II trial of pembrolizumab in subjects with previously systemically treated HCC. Three additional arms will be added as an amendment that will test pembrolizumab in combination with other experimental anti-cancer agents. The inclusion and exclusion criteria will be the same for each combination arm unless stipulated by one of the added agents. To be eligible, subjects must have documented objective radiographic progression after stopping treatment with sorafenib monotherapy, progression on sorafenib therapy, or intolerance to sorafenib, and have disease not amenable to a curative treatment approach (e.g., transplant, surgery, or ablation). Intolerance to sorafenib is defined as: National Cancer Institute (NCI) Common Terminology Criteria for Adverse Events (CTCAE), version 4.0 (Section 12.4) Grade  $\geq 2$  drug-related adverse event(s) (AE[s]) which both a) persisted in spite of comprehensive supportive therapy according to institutional standards and b) persisted or recurred after sorafenib treatment interruption of at least 7 days and a dose reduction and resulted in the subject requesting or the physician recommending discontinuation due to the toxicity. For Arm A, a subject who was treated on sorafenib as their last treatment may start pembrolizumab 14 days after the last dose of sorafenib. In order to be eligible, subjects must have at least 1 measurable lesion that is confirmed by M.D. Anderson radiology per Response Evaluation Criterion in Solid Tumors (RECIST) 1.1, Child Pugh status score of A, an Eastern Cooperative Oncology Group (ECOG) performance score of 0 or 1, and life expectancy of greater than 3 months. For Arm B, a subject with HCV who either progressed or did not tolerate sorafenib may start pembrolizumab and Zepatier as a second-line therapy 14 days after the last dose of sorafenib. In order to be eligible for Zepatier treatment, the subjects must have chronic HCV GT1 or GT4 and Child-Pugh class A liver disease. Subjects will be required to provide a tumor tissue sample at enrollment to support the correlative endpoints of the study. Approximately 15 subjects will be allocated to receive pembrolizumab 200 mg IV every 3 weeks (Q3W) and Zepatier orally (PO) once daily (qday) for 12 to 16 weeks depending on the HCV GT and prior HCV therapy as per prescribing information.

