### 3.1 Primary Objective(s)

- (1) **Objective: Arm A and Arm B:** To evaluate the tolerability of IV administration of pembrolizumab as second-line therapy in subjects with advanced HCC.
- (2) **Objective: Arm B:** To evaluate the efficacy of pembrolizumab in combination with Zepatier as assessed by the proportion of subjects with HCV GT1 or GT4 achieving Sustained Virologic Response 12 weeks after the end of all HCV study therapy (SVR12), defined as HCV RNA below the lower limit of quantitation (LLOQ) (either target detected unquantifiable [TD(u)] or target not detected [TND]) 12 weeks after the end of all study therapy.

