## 8.1 Statistical Analysis Plan Summary

Key elements of the statistical analysis plan are summarized in Table 15. The comprehensive plan is provided in Sections 8.2 to 8.13.

Table 15 Key Elements of the Statistical Analysis Plan

Study Design Overview	A Phase II Study of Pembrolizumab (MK-3475) in Hepatitis C Virus Positive and Negative Subjects with Advanced Hepatocellular Carcinoma Who Progressed on or Were Intolerant to First-Line Systemic Therapy
Treatment Assignment	This is a single arm open-label study.
Analysis Populations	Efficacy: All Subjects as Treated (ASaT) Safety: ASaT
Primary Endpoints	Correlative Biomarkers, Safety and Tolerability.
Statistical Methods for Key Efficacy Analyses	Objective Response Rate (ORR) based on RECIST 1.1 assessed by the MDACC imaging staff. The estimate of the ORR, along with its 90% confidence interval (CI) based on the Clopper-Pearson method (48), will be provided.
Statistical Methods for Key Safety Analyses	Counts and percentages of subjects with AEs will be provided.

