### 8.5.2 Safety Analysis Populations

The ASaT population will be used for the analysis of safety data in this study. The ASaT population consists of all allocated subjects who received at least one dose of study treatment.

At least one laboratory or vital sign measurement obtained subsequent to at least one dose of study treatment is required for inclusion in the analysis of each specific parameter. To assess change from baseline, a baseline measurement is also required.

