## 8.6 Statistical Methods

### 8.6.1 Statistical Methods and Data Analysis

This section describes the statistical methods that address the primary and secondary objectives.

This is a single arm, open-label exploratory Phase II study. Since no effective treatments are available in this setting, a response rate of 15% (within 95% CI) is considered acceptable (i.e., the signal for launching further, larger studies with pembrolizumab in this patient population is  $\geq 1$  response in the current study). If no response is observed, the treatment with pembrolizumab will be considered ineffective. A total of 15 patients will be enrolled and treated to rule out a response rate of 15% or less with 90% power when at least one response is observed. In other words, with 15 patients treated, the probability of observing at least one response is more than 90% if the response rate is at least 15% (Table 16). Descriptive statistics including with 90% confidence interval will be computed. Observed response profile, clinical benefit rate at 6 months and PFS along with relevant confidence intervals will be used to guide future development decisions.

Table 16 Analysis Strategy for Efficacy Variables

Total evaluable patients	Number of responders	Response rate	Lower 90% CI*	Upper 90% CI*
15	0	0%	<1%	18%
15	1	7%	<1%	27%
15	2	13%	2%	36%
15	3	20%	6%	44%
15	4	27%	10%	51%
15	5	33%	14%	58%
15	6	40%	19%	64%
15	7	47%	24%	70%
15	8	53%	30%	76%
15	9	60%	36%	81%
15	10	67%	43%	86%
15	>10**	>67%	>43%	>86%

\* Exact confidence interval computed by the method of Clopper and Pearson (Biometrika 26:404-413, 1934)

\*\*Actual response rate with corresponding CI will be calculated. Exact confidence interval was calculated for all responses.

Kaplan-Meier method will be used to compute the survival rate for the time-to-event endpoints such as PFS. The efficacy in biomarker subgroups will be summarized by descriptive statistics.

Table 17 Statistical Methods Per Endpoint Analysis

Endpoint/Variable (Description, Time Point)	Statistical Method	Analysis Population	Missing Data Approach
Primary Endpoint			

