## 8.9 Sample Size

In this study, approximately 15 subjects will be enrolled per Arm.

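### The DLT hold rule in section 8.6.2 is tied to combination therapy and names no counting unit, so on its literal wording the monotherapy arm has no boundary; it should be stated separately for Arm A and Arm B

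*Combined protocol and SAP*

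**What the plan says.** Section 8.6.2 calls a DLT rate of 30% or more excessive. It holds enrolment when the posterior probability that the rate exceeds 0.3 is above 0.8, under a beta(0.5, 0.5) prior. It turns this into counts: "This corresponds to withhold new patient entry when 3 DLTs are observed in 5 to 6 patients", then 4 in 7 to 9, 5 in 10 to 12 and 6 in 13 to 14. The stated chances of a hold are 0.02, 0.15, 0.41, 0.68 and 0.88 at true rates of 0.1 to 0.5. On who is counted, the section says only "DLTs will be assessed during the first cycle of combination therapy".

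Elsewhere:

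- Section 8.9: "In this study, approximately 15 subjects will be enrolled per Arm".
- Section 3.1, for both arms: "To evaluate the tolerability of IV administration of pembrolizumab as second-line therapy in subjects with advanced HCC".
- Section 1.0: Arm A is pembrolizumab alone; Arm B adds Zepatier, with ribavirin where its label calls for it.
- Section 8.1 (Table 15): "This is a single arm open-label study". Section 8.6.1: "A total of 15 patients will be enrolled and treated to rule out a response rate of 15% or less".
- Section 8.5.2: "The ASaT population consists of all allocated subjects who received at least one dose of study treatment".
- Section 8.6.2.1 places DLTs in Cycle 1 and relates them to study treatments, naming no arm. Item 8 lists IPI and PEG-INF, which neither arm receives. Item 10 speaks of three treatments, which can fit only Arm B subjects who also take ribavirin.
- Section 8.7: DLTs are analysed continuously during enrolment.

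**The concern.** This is the only numerical rule for holding enrolment in a trial whose primary endpoints include safety. Staff applying it after each subject must know whose DLTs go into the count, and three readings are open.

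1. **Per arm.** The boundaries end one short of an arm of 15.
2. **Arm B only.** This is the literal sense of combination therapy. It leaves Arm A unmonitored although tolerability is primary there too.
3. **Pooled.** The single-arm label and the single safety population could lead someone to keep one running count. A well-tolerated arm would then dilute DLTs in the other.

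The DLT list cannot settle the matter, because items 8 and 10 do not describe this trial's regimens. The printed hold probabilities also assume one DLT rate throughout, so they do not describe a mixed count.

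**Working it through.** **Inputs.** Threshold 0.3, cut-off 0.8, beta(0.5, 0.5) prior, boundaries and stated probabilities: section 8.6.2. Arm size 15: section 8.9. Looks after every subject: section 8.7. DLT rates of 30% and 40% are among the plan's own scenarios. The documents give no arm-specific rate or entry order, so Arm A at 5% to 30% and the orders below are assumptions.

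**Step 1: boundaries.** After x DLTs in n subjects the posterior is Beta(0.5 + x, 0.5 + n − x). Hold if P(rate > 0.3) > 0.8.

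- n = 5: x = 2 gives 0.703, x = 3 gives 0.923, so hold at 3.
- n = 9: x = 3 gives 0.604, x = 4 gives 0.830, so hold at 4.
- n = 12: x = 4 gives 0.614, x = 5 gives 0.814, so hold at 5.
- n = 14: x = 5 gives 0.690, x = 6 gives 0.853, so hold at 6.

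All printed boundaries from 5 to 14 are reproduced.

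**Step 2: the plan's hold probabilities.** Let q(n, k) be the probability of k DLTs after n subjects with no hold so far. Then q(n, k) = q(n−1, k)(1 − p) + q(n−1, k−1)p. At each look from 5 to 14, the mass at or above the boundary is removed and added to the hold probability. At p = 0.3 the first look contributes 10(0.3³)(0.7²) + 5(0.3⁴)(0.7) + 0.3⁵ = 0.1323 + 0.0284 + 0.0024 = 0.163; by n = 14 the total is 0.398.

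| True DLT rate | 0.1 | 0.2 | 0.3 | 0.4 | 0.5 |
|---|---|---|---|---|---|
| Stated | 0.02 | 0.15 | 0.41 | 0.68 | 0.88 |
| One run of 15, last look at 14 | 0.020 | 0.147 | 0.398 | 0.676 | 0.875 |
| Same, with a look at 15 (6 DLTs) | 0.021 | 0.154 | 0.422 | 0.710 | 0.900 |

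The second row matches to within about 0.01. The third misses at 0.4 and 0.5. The stated figures therefore describe one cohort of 15, the size of one arm.

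**Step 3: literal reading.** If only combination therapy is counted, no Arm A subject enters the rule. Arm A's hold probability at a 30% DLT rate is 0, against 0.398 with per-arm counting.

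**Step 4: pooled reading, Arm B at 40%.** The same recursion runs over 30 subjects, each with the rate of their arm. Continued means the posterior criterion is carried on to n = 29 (6 at 15, 7 at 16–17, 8 at 18–20, 9 at 21–23, 10 at 24–26, 11 at 27–29). The two values in a cell are for an Arm A subject first and an Arm B subject first.

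| Arm A rate | Alternating, printed boundaries | Alternating, continued |
|---|---|---|
| 5% | 0.153, 0.179 | 0.171, 0.212 |
| 10% | 0.228, 0.251 | 0.266, 0.305 |
| 20% | 0.384, 0.400 | 0.472, 0.499 |
| 30% | 0.538, 0.544 | 0.667, 0.679 |

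The per-arm comparator is 0.676. If all of Arm B entered first, the pooled value on the printed boundaries is also 0.676. If all of Arm A entered first, no printed boundary remains when Arm B starts. The chance of a hold during Arm B is then 0, or, with the criterion continued and given no hold in Arm A, 0.063 (Arm A at 10%) to 0.177 (Arm A at 20%).

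**Step 5: cost of per-arm counting.** With independent arms, P(at least one hold) = 1 − (1 − h)². At 20% in both arms: 1 − (1 − 0.1473)² = 0.273. At 10%: 1 − (1 − 0.0202)² = 0.040.

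**The case against.** The best answer is that the plan already means per arm. The boundaries and probabilities fit a run of 15, each arm has 15, and the arms are not to be compared. The total of 15 in section 8.6.1 cannot be a pooled 30. The safety population in section 8.5.2 defines an analysis set and not the denominator of an enrolment hold. Section 8.6.2.1 refers to Cycle 1 and study treatments without limiting DLTs to a combination, and the combination wording, like the drugs in item 8, looks carried over from elsewhere. All of this stands as evidence of intent. It does not remove the defect, because no sentence states the unit and the one phrase that describes the monitored treatment excludes Arm A.

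A reader might go further and infer that the plan pools the arms, or that pooling would cap Arm B's hold probability at some fixed low value. The documents support neither. The pooled figure depends on Arm A's DLT rate, entry order and whether the posterior criterion continues past 14; Step 4 runs from 0 to the full per-arm value.

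Nor do the documents say that Arm A fills first. Section 2.1 does say "It will commence as a single-arm, open-label, single-site Phase II trial of pembrolizumab in subjects with previously systemically treated HCC", but that sits beside arms to be added later by amendment. The current protocol already defines both arms, and section 3.0 separates them by HCV status.

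A large toxicity gap between arms is also unsupported. Section 5.2.1.4 puts Zepatier ALT elevations at about 1%, generally from week 8, outside Cycle 1. Ribavirin anaemia appears within 1 to 2 weeks (section 5.2.1.5) but concerns only those who take it.

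Other safeguards exist: treatment holds for hepatic events (5.2.1.3), termination on risk/benefit (5.9) and the investigator's review of aggregate data (7.2.4.3). They act on individual subjects or are qualitative, so they do not replace a boundary.

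**Conclusion.** The point holds as a defect in how the rule is written, not in its calibration: the boundaries and stated probabilities are sound for one arm of 15. The firmest consequence needs no assumption about entry order. On the literal wording Arm A has no boundary, which at a 30% DLT rate means a hold probability of 0 instead of about 0.40.

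The pooled consequence belongs to a weaker reading and is conditional. With Arm B at 40%, Arm A at 10% and alternating entry, the chance of a hold is 0.23 to 0.25 on the printed boundaries, or 0.27 to 0.30 with the criterion continued past 14, against 0.68 per arm. These rates and this order are illustrative. The change should be made because the rule governs subject safety and the correction is nearly free.

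**What to change.** In section 8.6.2, state that:

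- toxicity monitoring is applied separately in Arm A and Arm B;
- DLTs are assessed in Cycle 1 of that arm's study treatment (Arm A: pembrolizumab; Arm B: pembrolizumab plus Zepatier, with or without ribavirin);
- the boundaries count only that arm's subjects, and a hold applies to that arm only.

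In section 8.6.2.1, rewrite items 8 and 10 to name the drugs given in each arm, removing IPI, PEG-INF and the reference to three treatments. Section 10.6 can stay as it is: the hold rule does not depend on the summary described there.

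This takes a few sentences, with no new data and no change to the boundaries. The statistical price is two chances of a false hold: 0.27 for at least one arm if both true DLT rates are 20%, and 0.04 if both are 10%. Pembrolizumab DLTs seen in one arm would also not count towards the other arm's boundary.
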